5.1.1 Special circumstances for informed consent

A legally authorized representative may represent the subject during the informed consent process, which will be performed according to the requirements in section 5.1. The subject, if living, will also be informed about the clinical study within his/her ability to understand.

When obtaining informed consent from the subject is not possible because of the subject's medical condition, the Informed Consent of the subject's legally authorized representative will be requested.

In the event the subject has died, informed consent is not applicable. HIPAA compliance and other applicable federal, state and local laws will be reviewed by the center's IRB to determine the application of the Privacy Rule to a deceased subject's protected health information.

All other aspects of the informed consent process will be in compliance with section 5.1.

5.2 Point of Enrollment

Cohort 1

The presence of a fully executed informed consent form is required prior to each Emergency and Compassionate PIVSD procedure. These previously executed procedure informed consent forms contain language that allows for Sponsor data collection. All Emergency and Compassionate use patients will be included in Cohort 1, therefore, the point of enrollment is not defined for this cohort.

Cohort 2

A subject is considered enrolled in this study if the subject has been successfully implanted with the PIVSD Occluder; a post-procedure echocardiogram is able to be evaluated for residual shunt by the

Template: 86357 Rev. F Page 9 of 26

Clinical Investigation Plan

echocardiography core laboratory; and, for living subjects, the subject or the subject's legally authorized representative (LAR) has provided consent to participate in this study.

Potential subjects with PIVSD Occluder implants at study sites will be selected for screening of medical records followed by enrollment. For living subjects, upon obtaining consent, the Principal Investigator or delegated study personnel will record enrollment information (name of the clinical study and date of consent) in the hospital records and complete and submit an applicable CRF in a timely manner. For deceased subjects, the applicable CRF will be completed prior to sending the post-procedure echocardiogram for evaluation. Notification of subject consent (for living subjects only) to the Sponsor is considered to have occurred when the Sponsor has received the applicable CRF. However, the subject is not considered enrolled until a post-procedure echocardiogram is able to be evaluated for residual shunt by the echocardiography core laboratory.

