3.1.2 Device Description and Intended Purpose

The Amplatzer™ PIVSD Occluder is intended for percutaneous transcatheter closure of post-myocardial infarct muscular VSDs in patients who are not satisfactory surgical candidates. The occluder is implanted percutaneously to close post-myocardial infarct muscular VSD.

This confidential document is the property of Abbott and shall not be reproduced, distributed, disclosed or used without the express written consent of Abbott.

Template: 86357 Rev. F Page 5 of 26

Clinical Investigation Plan

The implant procedure is performed using a transcatheter approach under general anesthesia or conscious sedation, and can be performed in a catheterization laboratory setting under fluoroscopic and echocardiographic guidance.

The Amplatzer™ PIVSD Occluder is a self-expanding, double-disc device made from nitinol wire mesh (Figure 1) and designed to facilitate occlusion of muscular VSDs that occur post-myocardial infarction. The discs are linked together by a waist corresponding to the size of the VSD. To increase its closing ability, the discs and waist are filled with polyester fabric that is sewn securely to the device with polyester thread. Radiopaque marker bands at each end of the device provide visualization under fluoroscopy.

The Amplatzer™ PIVSD Occluder is designed to accommodate the damaged muscular tissue of the septal wall of myocardial infarction patients, and is available in five sizes: 16 mm, 18 mm, 20 mm, 22 mm, and 24 mm. All five device sizes have the same waist length of 10 mm.

The Amplatzer[™] TorqVue[™] system, which is 510(k) cleared, is used to deliver the Amplatzer[™] PIVSD Occluder. The delivery system consists of a delivery sheath with Touhy-Borst hemostatic adapter, dilator, loader, plastic vise, and delivery cable. A 9 Fr sheath is recommended for the 16 mm and 18 mm PIVSD occluders, and a 10 Fr sheath is recommended for the 20 mm, 22 mm, and 24 mm PIVSD occluders.

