4.4 Study Population

The intended population for the Amplatzer™ PIVSD Occluder is patients with post-myocardial infarct muscular VSD who are not satisfactory surgical candidates. The study will enroll subjects in two cohorts:

Cohort 1: All available Emergency and Compassionate PIVSD Occluder subject data from 2011 until the end of 2016 will be utilized to determine technical success, acute survival, and chronic survival. All subjects belonging to this cohort must have undergone an attempt to close a post-infarct VSD using the Amplatzer™ PIVSD Occluder.

Cohort 2: This cohort will consist of subjects over the age of 18 years who have previously been successfully implanted with the PIVSD Occluder and:

- for living subjects, the subject or subject's legally authorized representative has provided consent to participate in this study.
- the subject's post-procedure echocardiogram is evaluable and can be sent to the echocardiography core laboratory for residual shunt assessment.

Therefore, this cohort will be composed of retrospectively enrolled subjects. This cohort will be utilized to determine acute and chronic closure, and chronic survival.

5 Procedures

Approval from the Sponsor must be received prior to initiating study procedures. Baseline, procedure, post-procedure, and six month subject data will be collected retrospectively on each subject. The following sections provide a detailed description of procedures required by this CIP.

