5.3.2 Implant/Procedure and Post-Procedure

The following procedure information will be collected retrospectively via each subject's medical records:

- Date of procedure (if multiple procedures occurred, date of each procedure)
- Procedure success in a subject
- Implanted device(s) model number(s)
- Post-procedure echocardiogram obtained immediately after the successful deployment of the device and up to 7 days post-procedure is evaluable and can be sent to the echocardiography core laboratory for residual shunt evaluation.

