5.4 Study Flow Chart

The Figure 2 and the Table 3 below summarize subject flow and requirements of the study.

Figure 2: Cohort 2 Flow Chart

Template: 86357 Rev. F Page 11 of 26

Clinical Investigation Plan

Table 2: Cohort 2 Data Collection tests and procedures

VISIT	BASELINE	POST- PROCEDURE (UP TO 7	6 MONTHS* (>150 DAYS)	>6 MONTHS** (> 183 DAYS)
STUDY ACTIVITY		DAYS)		
Informed Consent Process				X
Demographics/Medical History	х			
Echocardiogram		Х	X*	

^{*}If subject was alive during the visit window

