6.1.1.1 Analysis Methods per Subject (Subject-Level Technical Success)

The proportion of subjects who experience technical success will be estimated.

Template: 86357 Rev. F Page 12 of 26

^{**}Since all data are retrospectively collected, informed consent occurs at 6 month or beyond the PIVSD occluder implant procedure

Clinical Investigation Plan

The 95% confidence interval for the rate of technical success will be calculated using the exact binomial method.

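### Entry to Cohort 2 is tied to vital status, so its 183-day survival estimate carries selection whose net direction cannot be determined

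*Combined protocol and SAP*

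**What the plan says.** Section 4.4 sets out what Cohort 2 is for: "This cohort will be utilized to determine acute and chronic closure, and chronic survival". Section 6.1.5.1 estimates 183-day survival by Kaplan-Meier with the procedure as Day 0, censors subjects whose status is unknown, and takes the interval from Greenwood's formula.

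Sections 4.4 and 5.2 give the entry conditions: a successful implant, a post-procedure echocardiogram that the core laboratory can evaluate and, for living subjects only, consent by the subject or a legally authorized representative. On the echocardiogram, section 5.2 says: "However, the subject is not considered enrolled until a post-procedure echocardiogram is able to be evaluated for residual shunt by the echocardiography core laboratory". Section 5.3.2 gives its window: "Post-procedure echocardiogram obtained immediately after the successful deployment of the device and up to 7 days post-procedure is evaluable".

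On timing, the footnote to Table 2 (section 5.4, printed after the page break under 6.1.1.1) says: "Since all data are retrospectively collected, informed consent occurs at 6 month or beyond the PIVSD occluder implant procedure". For deceased subjects, section 5.1.1 says: "In the event the subject has died, informed consent is not applicable". It also has the center's IRB review privacy law "to determine the application of the Privacy Rule to a deceased subject's protected health information". The visible text sets no minimum time since implant for a deceased subject.

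Cohort 1 also estimates 183-day survival. It takes all Emergency and Compassionate use patients from 2011 to the end of 2016, with consent executed before the procedure and no echocardiogram condition (sections 4.4, 5.1, 5.2). Section 5.1 allows such patients to be re-consented into Cohort 2.

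**The concern.** The clock starts at the implant, but membership of the cohort is decided later, by rules that depend on the outcome being measured. A patient alive at 6 months is counted only if reached and willing. A patient who died is counted without being asked and, as written, without waiting 6 months. A recently implanted patient can therefore enter as a death but not yet as a survivor. The scan requirement has no role in measuring survival, and it removes early deaths if those patients less often have a usable scan.

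Patients who never enter are absent from the data, not censored. Neither the censoring rule nor the Greenwood interval reflects them.

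Both safety endpoints are survival endpoints, and no adverse events are collected (sections 6.6.2 and 8.2). Cohort 1 stops at the end of 2016. In the visible text, implants after the January 2017 HDE approval are therefore covered only by Cohort 2. A reader of that survival figure could not tell how far it was shifted by who consented and who had a usable scan.

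**Working it through.** The visible text gives no sample size, expected survival, consent rate or scan rate, so there is no figure of the plan's own to reproduce. Every rate below is an assumption.

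**Model.** Let S be true 183-day survival, a the share of day-183 survivors who are enrolled, and b the share of patients dying before day 183 who are enrolled. With status known to day 183, the Kaplan-Meier estimate is a simple proportion:

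observed = S·a / (S·a + (1 − S)·b)

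There is no net bias when a = b.

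**At S = 0.50:**

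| Assumption | a | b | Observed |
|---|---|---|---|
| 70% of the living consent; all deaths enter | 0.70 | 1 | 0.35/0.85 = 41.2% |
| Same, but 20% of day-183 survivors die before screening and enter without consent | 0.2 + 0.8×0.7 = 0.76 | 1 | 0.38/0.88 = 43.2% |
| Scan only: 15% of patients die in week 1, half of them without a usable scan | 1 | (0.5 − 0.075)/0.5 = 0.85 | 0.5/0.925 = 54.1% |
| Scan only, and 20% of all other patients also lack one | – | – | 0.40/(0.40 + 0.28 + 0.075) = 53.0% |
| 70% consent, 20% of deaths lost | 0.70 | 0.80 | 0.35/0.75 = 46.7% |
| 80% consent, 20% of deaths lost | 0.80 | 0.80 | 50.0% |
| 70% consent, scan loss as above, 10% of deaths withheld for privacy | 0.70 | 0.9×0.85 = 0.765 | 0.70/1.465 = 47.8% |
| Same, 80% consent | 0.80 | 0.765 | 0.80/1.565 = 51.1% |

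**Other values of S.** 70% consent alone gives 0.21/0.91 = 23.1% at S = 0.30 and 0.49/0.79 = 62.0% at S = 0.70. The scan filter alone (S/0.925) gives 32.4% and 75.7%. At S = 0.70 this is a harsh case, because 15% dying in week 1 is half of all deaths.

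**Recent implants.** If N patients enter without selection and k recent implants enter only because the patient died, the numerator stays at S·N and the denominator becomes N + k. The estimate falls.

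**A wider grid.** I let consent and the share of deaths released each run from 0.6 to 1.0, scan availability in week-1 deaths from 0.3 to 0.9 (0.9 in everyone else), and the share of deaths falling in week 1 from 0.2 to 0.6. Observed survival then runs from 37.5% to 73.5% for a true 50%. The sign changes within the grid.

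**What bounds would look like (invented counts).** Take 40 implants, all at least 183 days before the cut-off. Thirty are enrolled, 14 of them alive at day 183: 14/30 = 46.7%. Ten are not enrolled: 3 declined, 2 died before day 183 without a scan, 2 are deceased with the date of death withheld, and 3 were not reached. Those who declined when approached were alive at day 183. The last two groups count as unknown.

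- Worst case: (14 + 3)/40 = 42.5%
- Best case: (14 + 3 + 2 + 3)/40 = 55.0%

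If the scan condition is dropped for survival, the 2 early deaths enter and the enrolled figure becomes 14/32 = 43.8%. The bounds do not move.

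**The case against.** The strongest reply is that no bias has been demonstrated. All rates are assumed, the filters pull in opposite directions, and some combinations cancel exactly. That stands. A reader might infer that survival is overstated, since patients must live long enough to be scanned. The documents do not support this: the scan may be taken immediately after deployment, on Day 0, and section 3.1.2 says the implant procedure "can be performed in a catheterization laboratory setting under fluoroscopic and echocardiographic guidance". The scan effect is then small, and the consent rule works the other way. A reader might equally infer that survival is understated, but that ignores the scan filter and any restricted records of deceased patients.

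It would also be too strong to call privacy clearance an entry condition. Sections 4.4 and 5.2 do not list it. It matters only if a center's IRB restricts a deceased patient's data.

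The consent effect is softened in two ways. A legally authorized representative may consent, and survivors of day 183 who die before screening enter without consent. If 20% of survivors do so, the three-filter case at 70% consent has a = 0.2×0.9 + 0.8×0.7 = 0.74 and gives 0.74/1.505 = 49.2% instead of 47.8%.

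Sampling error may be larger than the shift. In the example, the exact 95% interval for 14/30 is 28.3% to 65.7%, which contains the bounds of 42.5% to 55.0%. That limits the importance but does not answer the point, because selection does not shrink as more patients are enrolled.

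Emergency and Compassionate use patients who are in both cohorts offer a partial check through Cohort 1, but not for implants after 2016. Finally, sections 6.2 and 6.3 and Figure 2 are not visible, and section 4.1 breaks off after Cohort 1. Separate cohort reporting or a disposition table may be there, so their absence cannot be asserted.

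**Conclusion.** The point holds in a limited form. As written, entry to Cohort 2 depends on vital status through consent required of the living only, at 6 months or later, with no matching wait for the deceased. It also depends on a scan that the survival endpoint does not need. The resulting selection has a direction for each filter but no determinable net direction or size.

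Under the assumed rates at 50% true survival, single filters move the estimate to about 41% (43% with some later deaths) or about 54%, and together they can cancel. Section 6.1 states that no hypothesis is tested, so no decision rule is affected; the Cohort 2 survival estimate and its interval are. The structural finding rests on the text. Every percentage rests on assumption.

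**What to change.** 1. Make the evaluable echocardiogram a condition for the closure analysis sets only, not for Cohort 2 enrolment or the survival analysis.
2. Include only implants performed at least 183 days before a fixed screening cut-off, for living and deceased patients alike.
3. As far as each IRB allows, keep a site log of implanted patients who were not enrolled, by reason (declined, not reached, privacy restriction) and vital status. If the scan condition is kept, add lack of an evaluable scan as a reason. Report best-case and worst-case 183-day survival beside the Cohort 2 estimate.
4. Unless sections 6.2 and 6.3 already provide for it, report 183-day survival separately for the two cohorts, and identify patients who are in both.

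The cost is amended eligibility wording, one table, and a log of counts that needs IRB agreement. Section 5.2 already has sites screening the records of implanted patients, so the log extends an existing step. Some recent implants may be lost, and the reported survival range will be wider. Consent of living patients has to remain, so for that filter the remedy is disclosure through the bounds, not removal. A delayed-entry analysis would not substitute, because consent falls at about the end of the 183-day window or after it.

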5.3 Procedures

For Cohort 1, all available Emergency and Compassionate PIVSD Occluder subject data from 2011 until the end of 2016 will be utilized to determine technical success, acute survival, and chronic survival. Any available demographic/medical history information implant success and survival within 24 hours of the procedure and through 183 days post-procedure will be documented. No additional information will be collected in this cohort.

The Principal Investigator is responsible for ensuring all clinical study data is collected as required per CIP scheduled procedures.

5.3.1 Baseline

The following information will be collected retrospectively via subject's medical records:

- Date of myocardial infarct
- Demographics
- · Cardiovascular history and previous cardiac procedures
- · Risk factors and relevant comorbidities

5.3.2 Implant/Procedure and Post-Procedure

The following procedure information will be collected retrospectively via each subject's medical records:

- Date of procedure (if multiple procedures occurred, date of each procedure)
- Procedure success in a subject
- Implanted device(s) model number(s)
- Post-procedure echocardiogram obtained immediately after the successful deployment of the device and up to 7 days post-procedure is evaluable and can be sent to the echocardiography core laboratory for residual shunt evaluation.

5.3.3 Follow-up

The following data from at least 6-months post-procedure will be retrospectively collected:

- Survival assessment
- Implant status of PIVSD Occluder
- Echocardiogram (the echocardiography core laboratory will assess the residual shunt on this echocardiogram)

Template: 86357 Rev. F Page 10 of 26

[figure not shown]

Clinical Investigation Plan

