4.2 Objective

The objective of this clinical study is to evaluate the safety and probable benefit of the PIVSD Occluder in patients undergoing implantation of the PIVSD Occluder following an acute myocardial infarction.

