6.1.1 Effectiveness Endpoint 1: Technical Success

Technical success occurs when a subject is successfully implanted with a PIVSD device in the ventricular septal defect. An implant attempt occurs when the delivery system is inserted in the subject's vasculature.

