6.1.2 Effectiveness Endpoint 2: Acute Closure

Acute closure is defined as the absence of a residual shunt ≥3 mm, and will be assessed based on an echocardiogram obtained immediately after successful deployment and up to 7 days post-procedure.

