6.1.3 Effectiveness Endpoint 3: Chronic Closure

Chronic closure is defined as the absence of a residual shunt ≥3 mm at 6 months or later.

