6.1.4 Safety Endpoint 1: Acute Survival

[figure not shown]
Acute survival is defined as survival for at least 24 hours following an attempted PIVSD device implant.

Template: 86357 Rev. F Page 13 of 26

Clinical Investigation Plan

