6.1.5 Safety Endpoint 2: Chronic Survival

Chronic survival is defined as survival for at least 183 days from the time of first successful implant.

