6.6.2 Adverse Events

Data in this study are being collected retrospectively; therefore, no adverse event information will be collected. Additionally, these data do not apply towards any of the study endpoints. Mortality data will be collected to estimate survival.

Template: 86357 Rev. F Page 15 of 26

Clinical Investigation Plan

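### Cohort 2 implant status is collected at 6 months or later with no stated analysis, and chronic closure has no rule for a lost device or a re-closed defect

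*Combined protocol and SAP*

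**What the plan says.** Section 4.2 sets the objective: to "evaluate the safety and probable benefit of the PIVSD Occluder in patients undergoing implantation" after an acute myocardial infarction. Section 5.3.3 lists three follow-up items for retrospective collection from at least 6 months after the procedure: survival, an echocardiogram, and "Implant status of PIVSD Occluder".

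The five endpoints in 6.1 are defined as follows.

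- On technical success, 6.1.1 reads: "Technical success occurs when a subject is successfully implanted with a PIVSD device in the ventricular septal defect".
- For acute closure, 6.1.2 asks that no shunt of 3 mm or more be seen on an echocardiogram taken between deployment and day 7.
- On chronic closure, 6.1.3 reads: "Chronic closure is defined as the absence of a residual shunt ≥3 mm at 6 months or later". The analysis text in 6.1.3.1 adds that the core laboratory makes the reading and that time runs from the first successful implant.
- For acute survival, 6.1.4 asks that the patient be alive 24 hours after an implant attempt, whether or not it succeeded.
- On chronic survival, 6.1.5 reads: "Chronic survival is defined as survival for at least 183 days from the time of first successful implant".

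Section 4.4 assigns technical success, acute survival and chronic survival to Cohort 1, and acute closure, chronic closure and chronic survival to Cohort 2. Section 5.3 limits Cohort 1 to demographics and history, implant success and survival.

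On adverse events, 6.6.2 says: "Data in this study are being collected retrospectively; therefore, no adverse event information will be collected". It adds, as does 8.2, that such data bear on no endpoint.

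**The concern.** The study is meant to inform on device safety, yet both safety endpoints record only whether the patient is alive. With adverse events left out, implant status is the only listed follow-up item that shows directly whether the occluder is still where it was placed. The plan gathers it and then does not say what will be done with it. The retrospective design, given as the reason for omitting adverse events, does not explain this, because implant status is itself collected retrospectively.

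Two things are at stake. First, if known embolisations or explants exist in Cohort 2, reporting them is left to discretion. Second, chronic closure is presented as an effectiveness result for the occluder but is scored on residual shunt alone. A defect closed by a later operation or a different device would be credited to an occluder that is no longer there.

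**Working it through.** **Step 1. Where is implant status used?** I read each visible analysis and reporting section for it.

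- 6.1.1 to 6.1.5 (endpoints): not used.
- 6.4 (subgroups by sex): names only the five endpoints.
- 6.6.1 (baseline), 6.6.2 (adverse events), 6.6.3 (deviations): not used.
- 11 (progress reports): sites, enrolment and endpoint summaries only.
- 8.3 (complaints): covers only implants after HDE approval, goes to postmarket surveillance and feeds no endpoint.

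The visible numbering runs from 6.1.5.1 to 6.4, so I cannot speak for 6.2 and 6.3.

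**Step 2. How would a Cohort 2 patient with a lost device be scored?** The definitions are applied as written. The first three rows assume that the loss follows a qualifying echocardiogram showing closure and that the patient is alive at 183 days.

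| Course after loss | Acute closure | Chronic closure | Chronic survival | Reported as device loss? |
|---|---|---|---|---|
| Shunt of 3 mm or more at follow-up | success | failure | alive | no, only as a failed closure |
| Defect re-closed by surgery or another device | success | success | alive | no |
| No follow-up echocardiogram available | success | no reading | alive | no |
| Loss is fatal before 183 days | depends on timing | no reading | death | no, only as a death |
| Loss before the qualifying echocardiogram, shunt of 3 mm or more | failure | depends on course | depends on course | no, only as a failed closure |

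The second row is the clearest gap, because every endpoint the patient contributes to is favourable. The plan expects repeat procedures: 5.3.2 asks for the date of each one, and 6.1.3.1 counts from the first successful implant. It gives no scoring rule for them.

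**Step 3. Size.** The documents give no visible sample size, closure rate or device-loss rate, so there is no plan figure to reproduce. The numbers below are assumed and show scale only. The interval is the exact binomial one the plan already uses: lower limit = Beta quantile 0.025 with parameters (x, n − x + 1); upper limit = Beta quantile 0.975 with parameters (x + 1, n − x).

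Device in place among patients with known status, assuming 90%:

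- 18/20 = 90.0% (68.3% to 98.8%)
- 36/40 = 90.0% (76.3% to 97.2%)
- 54/60 = 90.0% (79.5% to 96.2%)

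With no losses at n = 20, 20/20 = 100%, with lower limit 0.025^(1/20) = 83.2%.

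Chronic closure, assuming 90% scored as closed and one of those patients re-scored as a failure (a change of 1/n):

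- n = 20: 18/20 to 17/20, that is 90.0% to 85.0% (62.1% to 96.8%), 5.0 points
- n = 40: 36/40 to 35/40, that is 90.0% to 87.5% (73.2% to 95.8%), 2.5 points
- n = 60: 54/60 to 53/60, that is 90.0% to 88.3% (77.4% to 95.2%), 1.7 points

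**The case against.** The strongest reply is that the endpoints already catch much of this. A lost device usually matters because the defect reopens, and a shunt of 3 mm or more at follow-up fails chronic closure on a core-laboratory reading. A fatal loss counts in survival. A loss before the qualifying echocardiogram would probably fail acute closure. All of that stands. A reader might infer from the unused field that device loss enters no endpoint at all; the definitions do not support that. What survives is that loss enters only indirectly, and not at all where the patient lives and the defect is re-closed.

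A reader might also infer that survival cannot reflect device loss because the disease is so lethal. Section 2 puts mortality on medical therapy alone above 90%. If anything this points the other way: loss without re-closure should tend to show in survival. Nor is it wrong for a survival endpoint to count survivors whatever their device status.

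Nor would one patient routinely score on technical success, acute closure and both survival endpoints. Those endpoints are split between cohorts, and one patient reaches all four only by being in both, which 5.1 allows for re-consented emergency and compassionate use patients.

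Finally, the study is descriptive, tests no hypothesis, declares its endpoints openly and answers to approval conditions that I cannot see. That limits the point to a reporting gap and a missing scoring rule. It does not explain why an item that is collected should go unsummarised.

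**Conclusion.** The point holds in limited form. The visible plan states no analysis of the Cohort 2 implant status it collects, and no rule for scoring chronic closure after explant, embolisation or re-closure. As written, a surviving patient whose device is lost after the qualifying echocardiogram is never reported as a device loss, and is a chronic closure success if the defect was re-closed by other means.

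The effect cannot be sized from the documents; the percentages above rest on assumed counts. The conclusion rests on the visible text and would change if 6.2 or 6.3 contained such an analysis. It does not extend to Cohort 1, where implant status at 6 months is not collected, so the summary proposed here would not alter technical success or acute survival.

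A reader might infer that technical success also needs a time point. That would not address later loss: a device lost on Day 2 would still count as successfully implanted at the end of the procedure, and the existing requirement that it be in the defect already covers loss during the procedure.

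This is a cheap improvement to the study's ability to answer its own safety question, not an error that invalidates the planned estimates.

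**What to change.** 1. Add to 6.6 a pre-specified Cohort 2 summary of the implant status collected under 5.3.3: in place, not in place, or unknown, with the reason for loss where the record gives it. Report the proportion in place among patients with known status, with an exact binomial 95% confidence interval, and show the number unknown beside it.
2. In 6.1.3 and Appendix B, score chronic closure as a failure when the study device is no longer in place or the defect was re-closed by surgery or another device; alternatively, report the rate both ways. State whether a second PIVSD Occluder counts as another device, since 5.3.2 allows for multiple procedures and devices.
3. Limit the safety conclusion to survival and, for Cohort 2, device retention.

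Implant status before death in patients who die before 6 months should not be added: 5.3.3 does not clearly collect it, and it would need new data.

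Cost: one table and a few sentences, using an item the plan already collects and an interval method it already specifies. The case report form is not in the documents, so how much detail it holds on the reason for loss, or on re-closure, is unknown; the summary should use what is recorded. The downside is that the chronic closure rate may fall slightly and a device-loss figure becomes public.
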